**SUMMARY OF CHANGES**

**PROTOCOL**

- **First Page, Protocol version and date change from v10 01/26/2022 to v11 08/18/2022**
- **First Page, added Funding sources**

Appendix 1 Dietary History Questionnaire for Microbiome Sampling

Appendix 2 Pathologic Response Assessment (irPRC Criteria)

## 1 Trial Summary

Trial Phase	Non-randomized phase II single arm Simon two-stage
Clinical Indication	PD-1 naïve stage IIIB/C/D melanoma
Trial Type	Neoadjuvant study
Type of control	Not applicable
Route of administration	CMP-001 pre-operatively (intra-tumoral) and post-operatively (subcutaneous) Nivolumab pre- and post- operatively (intravenous)
Trial Blinding	N/A
Treatment Groups	N/A
Number of trial subjects	Total sample size: 33 (1 st stage 14; 2 nd stage 16; 3 additional allowing for dropout)
Estimated enrollment period	15-20 months
Estimated duration of trial	24 months
Duration of Participation	24 months
Estimated average length of treatment per patient	52 weeks

## 2. Trial Design

### 2.1 Trial Design

This is a phase II single arm Simon two-stage single-center study of nivolumab in combination with Toll-like receptor 9 (TLR9) agonist CMP-001 in patients with PD-1 naïve stage IIIB-IIID cutaneous (or unknown primary) melanoma with clinically apparent lymph node (LN) and/or in-transit and/or satellite disease. The study will be conducted over a 52-week period.

Patients with stage IIIB-IIID cutaneous (or unknown primary) melanoma with palpable nodal disease and/or in-transit disease who have yet to undergo definitive surgery are eligible to enroll. Patients with nodal and/or in-transit relapse including those who have received prior adjuvant IFN and/or ipilimumab are eligible to enroll. However, patients who have received either nivolumab or pembrolizumab or ipilimumab/nivolumab are **NOT** eligible. Other eligibility criteria include, but are not limited to, absence of CNS disease and presence of disease amenable to biopsy.

Suitable patients will be identified pre-operatively. Patients will undergo a rapid (preferred 21 days, up to 28 days) screening evaluation consisting of systemic/CNS staging scans, tumor biopsy, and correlative blood studies to confirm suitability. Eligible patients will receive nivolumab/CMP-001 combination (prime phase) peri-operatively for a total of 7 weeks. In the peri-operative period, CMP-001 will be administered weekly via sub-cutaneous injection (week 1) then intra-tumorally (weeks 2-7). Following peri-operative therapy and restaging systemic scans, patients will undergo surgical resection. Post-operatively, patients will continue to receive nivolumab/CMP-001 combination (boost phase) every 2 (or 4) weeks (nivolumab) and 4 weeks (CMP-001) to complete 1 year (52 weeks) of therapy. In the post-operative period, CMP-001 will be administered subcutaneously.

## 2.2 Trial Diagram

[figure not shown]

Figure 1: Trial Diagram

### 3. Objective(s) and Hypothesis(es)

#### 3.1 Primary Objective and Hypothesis

**Objective:** To evaluate major pathologic response rate (MPR rate) in patients with stage IIIB/C melanoma following 7 weeks of nivolumab and injected CMP-001.

**Hypothesis:** That the combination of nivolumab and injected CMP-001 improves MPR rate in patients with stage IIIB/C melanoma.

#### 3.2 Secondary Objectives

**Objective:** To evaluate safety, relapse-free survival (RFS) and overall survival (OS) in patients with stage IIIB/C melanoma following 52 weeks of nivolumab/CMP-001 combination.

**Hypothesis:** Nivolumab/CMP-001 combination is safe and improves RFS and OS in patients with stage IIIB/C/D melanoma.

#### 3.3 Exploratory Objectives

**Objective:** To evaluate circulating and intra-tumoral immune cells, including T-cells (CD8, CD4, Tregs) and antigen-presenting cells (monocytes, macrophages, MDSCs), for the expression of inhibitory and activating receptors and ligands including functional analyses. To evaluate TCR clonality/diversity analyses of circulating and intra-tumoral CD8+ T-cells before and after nivolumab and CMP-001 combination. To evaluate genetic and transcriptomic signatures of response/non-response. To evaluate novel imaging characteristics in responders and non-responders.

**Hypothesis:** Nivolumab/CMP-001 combination improves T-cell functionality by augmenting antigen presentation and increasing T-cell infiltrate. Nivolumab/CMP-001 combination improves T-cell infiltrate by genetic, transcriptomic and imaging analyses.

#### **4. Background and Rationale**

##### **4.1 Background**

###### **4.1.1 Pharmaceutical and Therapeutic Background: Nivolumab**

The importance of intact immune surveillance in controlling outgrowth of neoplastic transformation has been known for decades (Disis 2010). The inability of the immune system to control tumor growth does not appear to result from an inability to recognize the tumor as foreign. Tumor cells have been shown to evade immune destruction despite displaying recognizable antigens on their surface and despite the presence of high-avidity T cells that are specific for these antigens (Boon and van der Bruggen 1996; Boon and Old 1997; Boon et al. 2006; Ercolini et al. 2005). Histologic evaluation of many human cancers show extensive infiltration by inflammatory and immune cells (Galon et al. 2006; Galon et al. 2012), suggesting that the immune system responds less effectively to malignancy. These observations have led to the hypothesis that dominant mechanisms of immune tolerance or immune suppression are responsible for the immune system's inability to effectively respond in a way that consistently results in rejection.

There are a number of inhibitory mechanisms that have been identified to be involved in tumor-mediated immune suppression and include expression of the programmed death ligand-1 (PD-L1), which can engage the inhibitory receptor PD-1 on activated T cells; the presence of the tryptophan-catabolizing enzyme IDO1, which exploits the exquisite sensitivity of T cells to tryptophan depletion and tryptophan metabolites; and infiltration with FoxP3+ regulatory T cells (Treg), which can mediate extrinsic suppression of effector T-cell function. Therefore, agents that target these negative regulatory pathways and thereby allow the expansion of effector T cells present in the tumor may be beneficial in the clinic.

The PD-1 receptor-ligand interaction is a major pathway stimulated by tumors to suppress immune control. The normal function of PD-1, expressed on the cell surface of activated T cells under healthy conditions, is to down-modulate unwanted or excessive immune responses, including autoimmune reactions. Programmed death receptor-1 (encoded by the gene *Pdcd1*) is an Ig superfamily member related to CD28 and cytotoxic T-lymphocyte-associated antigen-4 (CTLA-4), which has been shown to negatively regulate antigen receptor signaling upon engagement of its ligands (PD-L1 and/or PD-L2) (Freeman et al. 2000; Latchman et al. 2001; Liang et al. 2003). The mechanism by which PD-1 down modulates T-cell responses is similar to but distinct from that of CTLA-4, as both molecules regulate an overlapping set of signaling proteins (Parry et al. 2005; Hiraoka 2010).

Programmed death receptor-1 has been shown to be expressed on activated lymphocytes including peripheral CD4+ and CD8+ T cells, B cells, Tregs, and natural killer cells (Hodi et al. 2008). Expression has also been shown during thymic development on CD4-CD8- (double negative) T cells as well as subsets of macrophages and dendritic cells (DCs). The ligands for PD-1 (PD-L1 and PD-L2) are constitutively expressed or can be induced in a variety of cell types, including non-hematopoietic tissues as well as in various tumors (Latchman et al. 2001; Loke and Allison 2003; Liang et al. 2003; Francisco et al. 2009; Taube et al. 2014). Binding of either PD-1 ligand to PD-1 inhibits T-cell activation triggered through the T-cell receptor. PD-L1 is expressed at low levels on various non-hematopoietic tissues, most notably on vascular endothelium, whereas PD-L2 protein is only detectably expressed on antigen-presenting cells found in lymphoid tissue or chronic inflammatory environments. Programmed death ligand-2 is thought to control immune T-cell activation in lymphoid organs, whereas PD-L1 serves to dampen unwarranted T-cell function in peripheral tissues. Although healthy organs express little (if any) PD-L1, a variety of cancers were demonstrated to express abundant levels of this T-cell inhibitor. Programmed death receptor-1 has

been suggested to regulate tumor-specific T-cell expansion in subjects with melanoma (Liotta et al 2010). This suggests that the PD-1/PD-L1 pathway plays a critical role in tumor immune evasion and should be considered as an attractive target for therapeutic intervention.

Nivolumab is a fully human Ig G4 antibody that blocks PD-1. Nivolumab was initially approved by the FDA on December 22, 2014 for the treatment of patients with unresectable or metastatic melanoma and disease progression following ipilimumab and, if BRAF V600 mutation positive, a BRAF inhibitor. Nivolumab was also approved on March 4, 2015 to treat patients with advanced (metastatic) squamous non–small cell lung cancer (NSCLC) with progression on or after platinum-based chemotherapy. Additionally, FDA approved nivolumab on November 23, 2015 for advanced renal cell carcinoma. In Europe, it was approved on June 19, 2015 as a single agent (monotherapy) for the treatment of advanced (unresectable or metastatic) melanoma in adults. Another extension of indication was approved on October 28, 2015 to treat the advanced stages of squamous NSCLC after prior chemotherapy in adults. On February 25, 2016, it was also approved for advanced renal cell carcinoma after previous therapy in adults.

More recently, nivolumab was approved by the FDA (<https://www.fda.gov/Drugs/InformationOnDrugs/ApprovedDrugs/ucm590004.htm>) for the adjuvant treatment of resected stage IIIB-IVC melanoma patients on the basis of the data from the CheckMate-238 study (Weber et al. 2017). In this study, compared to ipilimumab, adjuvant therapy with nivolumab for 1 year resulted in significantly longer recurrence-free survival and overall survival. Compared to ipilimumab adjuvant therapy, nivolumab adjuvant therapy had a lower rate of grade 3 or 4 adverse events.

#### **4.1.2 Pharmaceutical and Therapeutic Background: CMP-001**

CMP-001 is a molecule comprised of a 30 nucleotide strand, flanked by 10 guanines on either end. The nucleotide strand is surrounded by a Q $\beta$  viral-like protein. The intended mechanism of action of CMP-001 in oncology is the activation of TLR9 in pDC within the tumor or the tumor-draining lymph nodes (tumor-associated pDC). Tumor-associated pDC activated by CMP-001 are expected to release large amounts of type I interferons (IFN), and increase their expression of costimulatory molecules and tumor antigen presentation to T cells, culminating in the generation of a clinically effective anti-tumor T cell response. In order for this response to be specific for the tumor, the pDC should have taken up the tumor antigens already, which requires them to be activated either within the tumor, or in the draining lymph nodes, which in turn requires the subcutaneous route of administration to reach a locally effective concentration of CMP-001. Systemic administration of TLR9 agonists results primarily in liver, spleen, and RES uptake with little specific activation of pDC in peripheral lymph nodes. Immature tumor-associated pDC contribute to tumor growth and an adverse prognosis in patients with cancer (Lombardi et al. 2015; Demoulin et al. 2013). Activating and maturing these pDC through either subcutaneous or intratumoral administration of CMP-001 is expected to reverse the pDC functional effects from promoting to antagonizing tumor growth, and from supporting immune tolerance to inducing an anti-tumor CD8+ T cell response in the tumor microenvironment.

CMP-001 is composed of (i) a virus-like particle (VLP) comprised of capsid proteins derived from bacteriophage Qbeta, which encapsulate (ii) a cytosine linked to a guanine by a phosphate bond (CpG) oligodeoxynucleotide (ODN) known as G10, which is a Toll-like receptor 9 (TLR9) agonist designed to induce high levels of type I interferon production and an anti-tumor CD8+ T cell response through activation of TLR9 in plasmacytoid dendritic cells (pDC). The therapeutic agent is a VLP referred to as QbG10. QbG10 has been previously studied in clinical trials under the name CYT003. In this protocol the name CYT003 will refer to historical data using the product in non-oncology settings. The name CMP-001 will refer to Checkmate Pharmaceuticals' plans for the agent.

#### 4.1.3 Preclinical and Clinical Trial Data: Nivolumab

Refer to the Investigator's Brochure for Preclinical and Clinical data.

#### 4.1.4 Preclinical and Clinical Trial Data: CMP-001

##### Preliminary Safety and Efficacy in Asthma

QbG10, currently known as CMP-001, has been previously studied in clinical trials under the name CYT003. CYT003 has been administered to 732 humans (volunteers or patients with non-cancer diagnoses) either alone or in combination with various allergens. CYT003 has been administered at doses as high as 2 mg weekly for seven doses by SC administration. CYT003 has reproducibly demonstrated evidence of TLR9 agonist activity with intended immune stimulatory effects. It has generally been well tolerated, with mild to moderate flu-like symptoms and/or injection site reactions noted in the majority of treated patients.

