##### Preliminary Safety and Efficacy in PD-1 primary Refractory Melanoma

Intratumoral administration of CMP-001 is currently being evaluated in combination with pembrolizumab in subjects with metastatic melanoma resistant to checkpoint inhibitors. In study CMP-001-001, A Multicenter, Open-label Phase 1b clinical Study of CMP-001 in Combination with Pembrolizumab in Subjects with Advanced Melanoma, CMP-001 is being administered intratumorally on a weekly (Schedule A) and Q3W schedule (Schedule B) across a dose range of 1-10 mg. To date, approximately 45 subjects have been treated in the CMP-001-001 study. Preliminary analysis of safety demonstrates an acute toxicity profile that predominantly consists of Grade 1-2 adverse events including mild fever, chills, rigors, nausea, vomiting and occasional hypotension. In some subjects the severity of this adverse event profile is increased. These AEs typically present after the third CMP-001 dose and generally resolve within a few hours with standard supportive care. The mechanism of action associated with the acute toxicity profile appears to resemble symptoms associated with cytokine release. A treatment algorithm has been developed for the management of these reactions and can be found in **Section 5.2.2.7.** CMP-001-001 adverse event summary in Cohort 2 of the Dose Escalation Phase are presented in **Table 4.1.4-1.**

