## **5.2.2 CMP-001 Dose Selection/Modification**

During the Prime Phase, the first dose of CMP-001 (week 1) is fixed at 5mg subcutaneously. Subsequent doses of CMP-001 administered during the Prime Phase (weeks 2-7) will be at 10mg administered intra-tumorally. Should patients develop side effects, intra-tumoral doses during this period of the Prime Phase (weeks 2-7) may be reduced (see **Table 5.2.2.3-1**).

Following resection, during the Boost Phase, the CMP-001 dose is fixed at 5mg injected subcutaneously at the site of the resected tumor.

Rationale for dose selection is provided in **Section 4.2.2 – Rationale for Dose Selection/Regimen/Modification: CMP-001**.

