### 8.2 Safety Monitoring

The PD-1/CMP-001 combination has been tested in the PD-1 refractory setting in melanoma including in a phase I study that evaluated multiple doses of CMP-001 including 5mg, 7.5mg and 10mg. The safety profile observed thus far suggests that the **risk of additive toxicities are unlikely to be significantly increased** in the neoadjuvant setting. Further, the dose being tested in this study (5mg) is 50% the ceiling dose tested in other CMP-001 studies in combination with PD-1 inhibitors, none of which reported a toxicity rate >33%.

However, in the context of this neoadjuvant trial, we will monitor dose limiting toxicities (DLTs) for 4 weeks for the 1st 3 patients accrued. DLT is defined as any adverse event(s) (AEs) considered possibly, probably, or definitely related to the CMP-001 plus nivolumab regimen, which occur during the first 15 days of therapy (i.e. following 3 doses of CMP-001; W1D1, W2D1, W3D1) IN the Prime phase only. Attribution of AEs specifically to either CMP-001 or nivolumab is challenging, therefore, the relationship to CMP-001 should be based on attribution to the combination of the two drugs. During DLT monitoring period, no further accrual will be permitted. Any patient who has started the studied treatment will be evaluable for safety.

The following AEs will be considered DLTs if deemed related to study therapy:

- Hematologic
  - Grade 4 neutropenia
  - Febrile neutropenia, defined as absolute neutrophil count (ANC)  $\leq 1000/\text{mm}^3$  with a temperature of  $\geq 38.3$  degrees °C
  - Grade  $\geq 3$  neutropenic infection
  - Grade  $\geq 3$  thrombocytopenia with bleeding
  - Grade 4 thrombocytopenia
- Non-hematologic
  - Grade  $\geq 3$  toxicities (non-laboratory)
  - Grade  $\geq 3$  nausea, vomiting or diarrhea despite maximal medical intervention
  - Grade 4 aspartate aminotransferase (AST) and alanine aminotransferase (ALT)

- Other (non AST/ALT) non-hematologic Grade  $\geq 3$  laboratory value if the abnormality leads to overnight hospitalization

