### **8.5 Safety Analysis**

As per NCI CTCAE Version 4.0, the term toxicity is defined as adverse events that are classified as either possibly, probably, or definitely related to study treatment. The maximum grade for each type of toxicity will be recorded for each patient, and frequency tables will be reviewed to determine toxicity patterns.

As CMP-001 has previously been dose-escalated in combination with PD-1 inhibitors pembrolizumab and nivolumab with minimal additional toxicities, no “dose-escalation” will be performed in this study. However, to accurately capture toxicities for this novel combination, we will be monitoring toxicities closely. The detailed data and safety monitoring plan is in **Section 8.7**.

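### Section 8.5 records the worst grade per toxicity type over all treatment with no split by phase, so toxicity of the subcutaneous Boost doses can disappear from the planned tables

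*Combined protocol and SAP*

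**What the plan says.** **Planned dosing (Section 5.2.2).** "During the Prime Phase, the first dose of CMP-001 (week 1) is fixed at 5mg subcutaneously". Then: "Subsequent doses of CMP-001 administered during the Prime Phase (weeks 2-7) will be at 10mg administered intra-tumorally". After surgery, "the CMP-001 dose is fixed at 5mg injected subcutaneously at the site of the resected tumor". Sections 6.1 and 7.1.1 give 12 Boost doses, one every 4 weeks over weeks 12-56.

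**Prior experience (Section 4.1.4).** In non-cancer subjects, "CYT003 has been administered at doses as high as 2 mg weekly for seven doses by SC administration". In the melanoma study, "CMP-001 is being administered intratumorally on a weekly (Schedule A) and Q3W schedule (Schedule B) across a dose range of 1-10 mg". Sections 8.2 and 8.5 also refer to earlier dosing with PD-1 inhibitors, including 5, 7.5 and 10 mg, but give no route.

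**Safety monitoring (Section 8.2).** DLTs are related events "which occur during the first 15 days of therapy", in Prime only, after the doses of weeks 1, 2 and 3.

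**Safety analysis (Section 8.5).** "The maximum grade for each type of toxicity will be recorded for each patient", and frequency tables are then reviewed. No period, phase or route is named, so the rule reads as covering all treatment.

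**Objective (Section 3.2).** Safety after 52 weeks of the combination is a secondary objective.

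**The concern.** The regimen has two very different parts: a short, weekly and mainly intra-tumoral Prime Phase, and a long subcutaneous Boost Phase at 4-week intervals after surgery. A single worst grade per toxicity type merges them. For the acute symptoms expected from CMP-001, a patient who already had the event in Prime adds nothing to the table if it recurs in Boost at the same or a lower grade.

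The Boost Phase is also where the protocol's stated experience is thinnest. The detailed oncology safety data in Section 4.1.4 are intra-tumoral, and the only earlier dose with a named subcutaneous route is 2 mg. No Boost dose falls in the DLT window. At stake is whether the planned output can show how the greater part of the 52-week regimen was tolerated.

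**Working it through.** **Inputs**
- Prime: 7 weekly CMP-001 doses; week 1 is 5 mg subcutaneous, weeks 2-7 are 10 mg intra-tumoral (Sections 5.2.2 and 6.1).
- Boost: 5 mg subcutaneous every 4 weeks, weeks 12-56 (Sections 5.2.2, 6.1 and 7.1.1).
- Highest earlier dose with a named subcutaneous route: 2 mg (Section 4.1.4).
- Related events on the weekly schedule in Table 4.1.4-1: fever 16/28, chills 15/28, hypotension 8/28.
- Planned patients: 30 evaluable, 33 in total (Section 8.3).

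**1. Boost dose count, the plan's own figure.** (56 − 12)/4 + 1 = 12. This agrees with Sections 6.1 and 7.1.1.

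**2. Share of doses by route.** Subcutaneous: 1 + 12 = 13. Total: 7 + 12 = 19. 13/19 = 68%. By amount the split is nearly even: 13 × 5 = 65 mg subcutaneous and 6 × 10 = 60 mg intra-tumoral, so 65/125 = 52%. These are planned counts. Section 5.2.2.8 lets a weeks 2-7 dose be omitted or given subcutaneously when the tumor is involuting.

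**3. Distance from the reported subcutaneous dose.** 5/2 = 2.5 times.

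**4. DLT coverage.** The window holds the doses of weeks 1, 2 and 3: one subcutaneous and two intra-tumoral. That is 1 of 13 subcutaneous doses and 0 of 12 Boost doses.

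**5. What the Section 8.5 rule keeps.** For one patient and one toxicity type, the recorded value is G = max(G_Prime, G_Boost). If G_Boost ≤ G_Prime, then G = G_Prime whatever happened in Boost. A patient with grade 2 fever in Prime is recorded as grade 2 whether the Boost fever was grade 0, 1 or 2. A Boost event of a new type, or of a higher grade, does show, but without a label saying when it occurred.

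**6. How many patients could be affected.** Assume that Prime rates equal the Table 4.1.4-1 weekly rates. Those come from intra-tumoral CMP-001 with pembrolizumab in advanced disease, so this is an illustration only. Among 30 patients:
- fever: 30 × 16/28 = 17.1
- chills: 30 × 15/28 = 16.1
- hypotension: 30 × 8/28 = 8.6

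In about 17 of 30 patients, a Boost fever of no higher grade would be invisible.

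**7. Denominator.** Under Sections 5.8 and 8.2, patients count for safety once treated, so the tables include patients never dosed in Boost. Suppose 19 of 33 have fever at some time (57.6%) and 25 enter Boost. The table then fits a Boost fever rate from 0/25 = 0% to 19/25 = 76%. With 30 entering Boost, the upper end is 19/30 = 63%. The overall rate is therefore no upper limit for the Boost rate. In the other direction, with 25 of 33 entering Boost, toxicity first seen in Boost is shown at 25/33, or about three quarters, of its rate among those dosed there.

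The dose count rests on Sections 5.2.2, 6.1 and 7.1.1. Section 8.1 describes Prime CMP-001 as intra-tumoral throughout, and Section 4.2.2 words the Boost interval and duration differently. Those passages must be reconciled with the schedule.

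**The case against.** The strongest reply is that this is a gap in table layout and not in safety oversight. Several parts of it are sound.

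- **The rule works by toxicity type.** New or worse toxicity in Boost still appears. This stands and limits the loss to repeat events of equal or lower grade, plus dilution.
- **The data exist.** Section 7.2.4 records onset and resolution date and time, and Section 7.2.2.4 records actions on each drug separately. A reader might infer that subcutaneous toxicity cannot be learned from this trial. The documents do not support that: only the planned tables fail to show it.
- **Other safeguards run through Boost.** Each injection has at least 1 hour of observation (Section 5.2.2.6), injection-site skin events are reported as events of clinical interest (Section 7.2.5.2), and review is weekly and monthly (Section 8.7). These stand as monitoring. None specifies an analysis by phase, and the events of clinical interest do not include fever, rigors or hypotension as such.
- **The first 5 mg subcutaneous dose is inside the DLT window**, a week before nivolumab and intra-tumoral dosing begin. This is true, but it is a first exposure. Section 4.1.4 places the typical acute reactions after the third dose, and Section 4.2.2 says antibodies form after the first. Week 1 is weak evidence for later subcutaneous doses.
- **Subcutaneous experience may go beyond 2 mg.** A reader might infer that it stops there. Sections 8.2 and 8.5 refer to other earlier dosing without a route, so the documents settle only that 2 mg is the highest dose reported with that route named. A historical maximum and a larger planned dose are also not in themselves a contradiction.
- **Tables by period do not isolate route.** This stands in full. Route is mixed with surgery, dosing interval, nivolumab schedule and prior exposure; some weeks 2-7 volume may be given peri-tumorally; and Section 7.2.2.2 attributes events to the combination.

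**Conclusion.** The point holds as a gap in the planned safety summary. Section 8.5 discards Boost information exactly where the same acute symptoms are likely in both phases, and it has no denominator of patients dosed in Boost. The part of the regimen concerned is 12 of 19 doses; with week 1, 13 of 19 (68%) are 5 mg subcutaneous, 2.5 times the only earlier dose reported with that route named.

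How much is hidden cannot be fixed from the documents. It depends on Prime event rates, on how many patients reach Boost and on how often events recur; the counts of 17 of 30 and 19 of 25 above are illustrations under stated assumptions. The loss is certain only for repeat events of the same type at equal or lower grade.

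The primary endpoint and its decision rule are untouched. Nothing here shows that the subcutaneous dose is unsafe, and a reader should not infer it. The change should be made because it serves the 52-week safety objective and costs very little.

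**What to change.** **Section 8.5.** Keep the overall tables. Add the worst grade per toxicity type per patient for each of three periods:
1. week 1 (subcutaneous);
2. weeks 2-7 (mainly intra-tumoral);
3. Boost (subcutaneous).

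Use as denominator the patients given CMP-001 in that period, and print it. Assign events by the onset date already collected, and state where events in the interval around surgery are counted. Label these tables descriptive, and say that differences between periods are not route effects.

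**Section 8.2.** State the prior CMP-001 experience by route. Reconcile the statement there that the dose under test is 5 mg with Section 5.2.2, which plans 10 mg intra-tumorally in weeks 2-7. No dose is proposed here.

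**Cost.** Three extra tables with smaller counts, and a short addition to Section 8.2. No new data, visits or patients are needed.
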